3.3 Inclusion of Women and Minorities

Both men and women of all races and ethnic groups are eligible for this trial. This study will not select subjects based on sex/gender and racial/ethnic group members.

4. STUDY PROCEDURES

	Screening/ Baseline ⁹	¹¹¹ In- XYIMSR-01 Dosing and SPECT/CT Imaging	¹¹¹ In-XYIMSR-01 SPECT/CT	Follow-Up visit
	Day-30 to Day 1	Day 1	Day 2, and Day 3 post-injection (24± 1 hour, and 48± 1 hour post-injection)	Within 7 Days from ¹¹¹ In-XYIMSR-01 Administration
Informed Consent & Eligibility	X			
Demographics (date of birth, race, ethnicity)	X			
Medical History	X			
Vital Signs (Blood Pressure, Heart Rate, Temperature) ¹	X	X ¹	X	
Height and weight	X	X	X	
Clinical Labs (Hematology, Chemistry) ²	X	X	X ¹⁰	
Urinalysis	X			
Pregnancy test ³	X	X		
Study Sample Collection ⁴		X		
12-Lead Electrocardiogram (ECG)	X	X ⁵	X ¹¹	
¹¹¹ In-XYIMSR-01 Administration ⁶		X		
SPECT/CT ⁷		X	X	
Adverse Events		X	X	X
Concomitant Medications	X	X	X	X
Standard-of-care Conventional Imaging Review	X			X
Standard-of-care Archived Tumor Tissue or Recent Tumor Biopsy	X			
Follow-Up phone call ⁸				X

¹ On Day 1 Vital Signs (Blood Pressure, Heart Rate, Temperature) will be performed before ¹¹¹In-XYIMSR-01 Administration injection and at the end of ¹¹¹In-XYIMSR-01 SPECT/CT

² Standard of care comprehensive metabolic panel to include measurement of sodium, potassium, chloride, bicarbonate, BUN, creatinine, glucose, total bilirubin, calcium, total protein, albumin, AST, ALT, and alkaline phosphatase.

Standard of care CBC: WBC differential (neutrophils, lymphocytes, monocytes, eosinophils, basophils), WBC count, RBC count, Hematocrit, Hemoglobin, Platelets.

³ For females of childbearing potential, a negative serum or urine pregnancy test will be obtained within a 24-hour period prior to SPECT/CT study.

⁴ Blood samples will be collected at the following time points: pre-dose, 5±2 minutes, 10±2 minutes, 20±5 minutes, 30±5 minutes, 1±0.25 hour, 1.5±0.25 hour, and 24 hours ± 1 hour, post-injection to estimate elimination half-life. About 5 mL of blood will be collected in a heparinized tube at each time point via a peripheral vein.

⁵ A 12-lead electrocardiogram will be performed just prior to ¹¹¹In-XYIMSR-01 administration and immediately following SPECT/CT imaging

⁶ Patients will receive 10.5±1 mCi of radiotracer via an intravenous catheter placed in an antecubital vein or an equivalent venous access.

⁷ SPECT/CT will be acquired at 2-4, 24± 1 hour, and 48± 1 hour post-injection. For the first three enrolled patients, a total of three fields of view will be acquired and for the remaining 7 patients two fields of view will be acquired. Each SPECT acquisition will be acquired over a 20-30 minute period.

⁸ A safety phone call will also occur 7(±3) days post-dosing. Ongoing adverse events thought to be related to ¹¹¹In-XYIMSR-01 will be followed until resolution of the adverse event, until an alternate cause has been identified, the patient is lost to follow-up, the patient withdraws consent, or it has been determined that ¹¹¹In-XYIMSR-01 is not the cause of the adverse event.

⁹ In order to minimize the need for research-only in-person visits, telemedicine visits may be substituted for in-person research study visits or portions of research study visits where determined to be appropriate and where determined by the investigator not to increase the participants' risks. Prior to initiating telemedicine for study visits the study team will explain to the participant, what a telemedicine visit entails and confirm that the study participant is in agreement and able to proceed with this method. Telemedicine acknowledgement will be obtained in accordance with the Guidance for Use of Telemedicine in Research. In the event telemedicine is not deemed feasible, the study visit will proceed as an in-person visit. Telemedicine visits will be conducted using HIPAA compliant method approved by the Health System and within licensing restrictions.

¹⁰ Safety blood tests: comprehensive metabolic panel to monitor blood chemistries, including kidney and liver function, and blood cell count will be collected at the end of 48 hour SPECT/CT imaging.

¹¹ A 12-lead electrocardiogram will be conducted at the end of 48 hour SPECT/CT imaging.

Pharmacokinetics & Imaging Timepoints:

Procedure	Pre-dose	0 hour	5± 2min.	10± 2 min.	20± 2 min.	30± 5 min.	60± 25 min.	90± 25 min.	2-4 hour	24± 1 hour	48± 1 hour
¹¹¹ In-XYIMSR-01 Administration		X									
Blood & Plasma Collection	X		X	X	X	X	X	X		X	
¹¹¹ In-XYIMSR-01 SPECT/CT Imaging									X	X	X

5. CRITERIA FOR DISCONTINUATION: CANCELLATION/WITHDRAWL PROCEDURES AND EARLY STOPPING RULES.

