1. BACKGROUND

1.1 Study Disease(s)

Renal cell carcinoma (RCC) & Carbonic Anhydrase IX (CAIX): Renal cell carcinoma (RCC) is the most common neoplasm of the kidney [1], with an estimated 60,000 patients diagnosed annually in the United States [2]. Among cases of RCC, the clear cell subtype (ccRCC) is the most prevalent, accounting for up to 70% of RCCs [3–5]. Common to ccRCC is loss of the Von Hippel-Lindau (*VHL*) tumor suppressor gene [6]. Loss of *VHL* in turn leads to over-expression of carbonic anhydrase IX (CAIX) [7], a membrane-associated enzyme responsible for catalyzing the reversible hydration of carbon dioxide to a bicarbonate anion and a proton [8, 9]. Overexpression of CAIX is known to be presented in approximately 95% of ccRCC tumor specimens [10–12], making it a useful biomarker for this disease.

CAIX has limited expression in normal tissues with the exception of the gastrointestinal tract, gallbladder and pancreatic ducts [8, 9, 13–15]. Feasibility for the non-invasive detection of ccRCC based on CAIX expression has been proved with the radiolabeled antibody G250 [16] and its potential clinical applications has been reviewed previously [17]. However, antibodies as molecular imaging agents suffer from pharmacokinetic limitations, including slow blood and non-target tissue clearance (normally 2–5 days or longer) and non-specific organ uptake. Low molecular weight agents demonstrate faster pharmacokinetics and higher specific signal within clinically convenient times after administration. Low molecular weight agents can also be synthesized in radiolabeled form more easily, and may offer a shorter path to regulatory approval [18].

Targeting CAIX with small molecule inhibitors has proved challenging in part because there exists fifteen human isoforms of carbonic anhydrase. These isoforms share common structural features, including a zinc-containing catalytic site, a central twisted β -sheet surrounded by helical connections, and additional β -strands. The isoforms, however, vary widely in terms of intracellular location, expression levels, and tissue distribution [8, 9]. Significant effort has been expended on the development of sulfonamides and other low molecular weight CAIX ligands for nuclear imaging, but most reported agents have been fraught with low tumor uptake and significant off-target accumulation [19–24].

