2. OBJECTIVES

2.1 Primary Objectives:

The primary objective of this study is to evaluate the safety, tolerability, and feasibility of ^{111}In -XYIMSR-01 SPECT/CT in patients with metastatic ccRCC.

2.2 Secondary Objectives:

- To determine the biodistribution and radiation dosimetry of ^{111}In -XYIMSR-01.
- To characterize the pharmacokinetics of ^{111}In -XYIMSR-01.
- To assess the concordance of findings on ^{111}In -XYIMSR-01 SPECT/CT with conventional imaging.

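### No Day 1 vital signs or ECG are scheduled between injection and the end of the 2-4 h SPECT/CT, so early safety rests on adverse event observation alone

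*Combined protocol and SAP*

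**What the plan says.** Section 2.1 opens: "The primary objective of this study is to evaluate the safety, tolerability, and feasibility of" the tracer's SPECT/CT in metastatic clear cell disease. Section 7.1 assesses this through adverse events graded by CTCAE version 5.0.

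The Day 1 measurements are timed in the footnotes to the Section 4 calendar:

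- **Vital signs, footnote 1:** "On Day 1 Vital Signs (Blood Pressure, Heart Rate, Temperature) will be performed before" the injection, and again when the SPECT/CT ends.
- **ECG, footnote 5:** "A 12-lead electrocardiogram will be performed just prior to" dosing, and then "immediately following SPECT/CT imaging".
- **Scan, footnote 7:** "SPECT/CT will be acquired at 2-4, 24± 1 hour, and 48± 1 hour post-injection". The first three patients have three fields of view and the other seven have two. "Each SPECT acquisition will be acquired over a 20-30 minute period".
- **Blood samples, footnote 4:** six Day 1 draws after injection, at 5, 10, 20, 30, 60 and 90 minutes. Section 7.2 has them assayed for radioactivity, protein binding and metabolites.

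The calendar also marks adverse events and clinical labs on Day 1. The labs have no stated time relative to injection. Section 8.1 relies on the calendar for close monitoring of patients. Section 8 collects events that the patient reports, that questioning brings out, or that laboratory tests or other means detect.

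**The concern.** A site that follows the calendar exactly takes no scheduled blood pressure, heart rate, temperature or ECG reading from injection until the first scan is over. A patient can report a symptom, and staff can ask about one. Neither route reveals a short-lived change in blood pressure or heart rate that the patient does not feel. If such a change resolves before the end of the scan, the record shows a normal pre-injection value and a normal post-scan value.

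A finding of good tolerability would then partly reflect when patients were measured. Nothing else in the documents covers the gap. The rat endpoints listed under Toxicology in Section 1 are survival, clinical signs, body weight, laboratory parameters, organ weights and histopathology; blood pressure, heart rate and ECG are not among them. No human data on this agent are cited. Section 7.1 refers only to experience with other radiotracers given at similar doses. Early readings that were not taken cannot be recovered later.

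**Working it through.** **The plan's own figure.** Section 7.1 says that 0 events in 10 patients gives 90% confidence in a rate between 0% and 25%. The exact two-sided 90% upper limit is 1 − 0.05^(1/10) = 0.259, or 25.9%, which agrees to within a point. This figure concerns radiotracer-related grade 3-5 events and is not in dispute. It takes for granted that every such event is detected.

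**Time of the first post-injection reading.** First reading = scan start + SPECT acquisition time. Footnote 7 does not say whether 2-4 h is the start or the whole session, nor whether 20-30 minutes applies to each field or to all fields together. CT and positioning time is not given and is left out.

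1. 2-4 h is the start, 20-30 min per field, two fields (seven patients):
   - earliest 120 + 2 × 20 = 160 min (2 h 40 min)
   - latest 240 + 2 × 30 = 300 min (5 h)
2. The same reading with three fields (first three patients):
   - earliest 120 + 3 × 20 = 180 min (3 h)
   - latest 240 + 3 × 30 = 330 min (5 h 30 min)
3. 2-4 h is the start, 20-30 min covers all fields:
   - earliest 120 + 20 = 140 min (2 h 20 min)
   - latest 240 + 30 = 270 min (4 h 30 min)
4. 2-4 h bounds the whole session: the reading comes no later than about 240 min (4 h).

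Across these readings the gap ends between 2 h 20 min and 5 h 30 min. No reading removes it, and it applies to all 10 patients.

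**Contacts inside the gap.** The last early draw is at 90 minutes. Its tolerance is 0.25 h in footnote 4 and 25 min in the time-point table. At the wider tolerance it falls at 90 + 25 = 115 min, before the earliest scan start of 120 min. All six draws therefore lie inside the gap, and none has a vital sign attached.

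**Other scheduled safety data.** Day 1 labs might fall in the gap, but they are untimed and do not measure blood pressure or heart rate. Vital signs on Days 2 and 3 and the ECG after the 48 h scan come later still.

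**The case against.** The strongest reply is that the primary safety measure is the graded adverse event, not the vital sign. Adverse events are marked on Day 1, Section 8.1 promises close monitoring, and staff are with the patient six times in the first 90 minutes. Rats at 11 and 55 µg/kg showed no consistent or treatment-related effects. The plan contains no contradiction here, so asking for earlier readings can be called a design preference.

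Much of this stands. Three stronger readings are tempting, and the documents support none of them:

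- **That the primary objective goes unmeasured in this interval.** It does not: adverse event collection covers it. What is missing is any scheduled vital sign or ECG.
- **That the 0-of-10 statement or the pause rule in Sections 5.4 and 7.3 is compromised.** Both concern related grade 3-5 events. Nothing shows that a brief change without symptoms would reach that grade.
- **That one can calculate how much of an early effect would have faded by the first reading.** The documents give no duration for any such effect, no human pharmacokinetics and no injection duration. The remark in Section 1.1, "Low molecular weight agents demonstrate faster pharmacokinetics", contrasts small molecules with antibodies and says nothing about acute cardiovascular effects. An early peak in blood level is plausible for an intravenous agent, but it is an inference.

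The reply does not cover a change that produces no symptom. Section 8's other means could include a reading taken ad hoc, but nothing schedules one.

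**Conclusion.** The concern holds as a gap in scheduled measurement. In all 10 patients, vital signs and ECG are unscheduled from injection until the end of the first scan. That is at least about 2 h 20 min and at most about 5 h 30 min (5 h for the seven patients with two fields), counting SPECT acquisition time only and depending on how footnote 7 is read. In that interval, early safety rests on adverse event observation, which can miss a transient blood pressure or heart rate change without symptoms.

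The likelihood of such a change cannot be estimated from the documents, and no effect on the grade 3-5 count is shown. The case for acting is that safety and tolerability are primary, no human data on this agent are cited, the listed rat endpoints omit these measures, and the remedy is cheap.

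**What to change.** Amend footnote 1 so that vital signs are also recorded at some of the Day 1 blood draws already scheduled between 5 and 90 minutes. Keep the end-of-scan readings, and report change from the pre-injection value at each time. The sponsor should choose the draws. The 20, 60 and 90 minute tolerances differ between footnote 4 and the time-point table, so they need to be reconciled before readings are tied to them. Footnote 7 should also say whether 2-4 h is the start time and whether 20-30 minutes is per field.

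If early vital signs are not added, the safety conclusion should state that vital signs and ECG were not assessed before the end of the first scan. No additional ECG is requested. If only vital signs are added, the same statement should be made for ECG.

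The cost is a few minutes of staff time at existing contacts and an amendment to the footnotes, with no added visit. This changes data collection only and sets no management rule.

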3.2 Eligibility Criteria

Inclusion Criteria:

1. Males or female sex
2. ≥ 18 years of age
3. Willingness to provide signed informed consent and comply with all protocol requirements
4. Histological confirmation of RCC with a clear cell component
5. 2-10 sites of disease measuring ≥ 1.5 cm on contrast-enhanced CT and/or MRI imaging of the chest, abdomen and pelvis performed ≤ 60 days prior to the date of study enrollment
6. Screening clinical laboratory values as specified below:
 - Serum bilirubin ≤ 1.5 times the upper limit of normal. For patients with known Gilbert's syndrome, $\leq 3 \times \text{ULN}$ is permitted
 - ALT ≤ 3 times the upper limits of normal
 - AST ≤ 3 times the upper limits of normal
 - Creatinine clearance ≥ 50 mL/min based on Cockcroft-Gault formula
 - Absolute neutrophil count $\geq 1,500 / \text{mm}^3$
 - Platelets $\geq 100,000 / \text{mm}^3$
 - Hemoglobin $\geq 9.0 \text{ g/dL}$
 - White blood cell count $\geq 2,000 / \text{mm}^3$

Exclusion criteria:

- Systemic therapy for the treatment of ccRCC within 12 months of study enrollment.
- Subjects administered any radioisotope within five physical half-lives prior to study drug injection.
- Subjects with any medical condition or other circumstances that, in the opinion of the investigator, compromise obtaining reliable data, achieving study objectives, or completion.
- Women of child-bearing potential (WOCBP) must have a negative serum or urine pregnancy test (minimum sensitivity 25 IU/L or equivalent units of human chorionic gonadotropin) within 24 hours prior to the imaging day.
- Women must not be breastfeeding.

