6.1.1 Drug Substance

Common Name: ^{111}In -XYIMSR-01

Unit Dose: 10.5 ± 1 mCi of ^{111}In -XYIMSR-01 followed by SPECT/CT imaging

Route of administration: Intravenous catheter placed in an antecubital vein or an equivalent venous access

6.1.2 ^{111}In -XYIMSR-01 Manufacturer

The radiotracer will be manufactured at the Center for Translational Molecular Imaging located

at [name].

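### The pregnancy-test rules in section 3.2 and footnote 3 contradict each other, and neither refers to the radiotracer injection

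*Combined protocol and SAP*

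**What the plan says.** The combined protocol and SAP times the pregnancy test in three places.

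- Section 3.2, in the exclusion list, requires a negative result "within 24 hours prior to the imaging day". The imaging day is not defined.
- The calendar in section 4 has a row "Pregnancy test ³" marked twice: under Screening/Baseline (Day -30 to Day 1) and under Day 1, the day of both dosing and first imaging. The row "Informed Consent & Eligibility" is marked under Screening/Baseline only.
- Footnote 3, attached to the pregnancy-test row, says that "a negative serum or urine pregnancy test will be obtained within a 24-hour period prior to SPECT/CT study".

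The order of events is clear. Footnote 7 states "SPECT/CT will be acquired at 2-4, 24± 1 hour, and 48± 1 hour post-injection", and section 6.1.1 describes the dose as "followed by SPECT/CT imaging".

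Other items are tied to dosing. Footnote 5 begins "A 12-lead electrocardiogram will be performed just prior to" and goes on to name administration. Footnote 1 places the first Day 1 vital signs before the injection. The radioisotope exclusion in section 3.2 counts back from the study drug injection. The pregnancy test has no such anchor in either rule.

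**The concern.** Exposure to the radiotracer begins at injection, not at the scan. A rule that counts back from the scan leaves open which comes first on Day 1, the test or the dose. A second rule that counts back from a calendar day gives a different set of acceptable tests.

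Two things are at stake. A site following the calendar and footnote 3 could carry out the Day 1 test after dosing; under section 5.1 a participant can no longer be cancelled once the drug has been given, so a positive result at that point comes too late for that route. And a site that tests on the morning of Day 1, as the calendar invites, does not meet section 3.2 as literally worded and may record an avoidable eligibility deviation.

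**Working it through.** The plan gives no figure to reproduce. The check sets the two windows on one time axis.

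**Inputs.** Injection = 0 h. First scan at g = 2 to 4 h (footnote 7). Footnote 3 window: the 24 h before the scan. Section 3.2 window: the 24 h before the imaging day, taken as Day 1 starting at midnight. Assumption: the documents give no clock time, so injection is placed at t = 08:00 to 12:00.

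**Footnote 3 alone.** The window runs from g - 24 to g.
- g = 2: from -22 h to +2 h; 2/24 = 8.3% lies after injection.
- g = 4: from -20 h to +4 h; 4/24 = 16.7% lies after injection.

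**Section 3.2 alone.** The window closes at midnight, so the latest acceptable test is t hours before injection, that is 8 to 12 h. None of the window lies after injection.

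**One test meeting both rules.** The scan is at clock time s = t + g, from 8 + 2 = 10:00 to 12 + 4 = 16:00. The common window runs from s - 24 to midnight and lasts 24 - s: between 24 - 10 = 14 h and 24 - 16 = 8 h, all on the day before Day 1.

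**Earliest test allowed by section 3.2.** It is 24 + s before the scan: 34 to 40 h, outside footnote 3.

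| Time of test | Section 3.2, imaging day = Day 1 | Footnote 3 | Calendar column |
|---|---|---|---|
| Day before, more than 24 h before the scan | meets | fails | Screening/Baseline |
| Day before, within 24 h of the scan | meets | meets | Screening/Baseline |
| Day 1, before injection | fails | meets | Day 1 |
| Day 1, after injection, before first scan | fails | meets | Day 1 |

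No test done on Day 1 meets section 3.2 literally, although the calendar schedules one.

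**Looser reading of section 3.2.** If it is taken to mean 24 h before imaging, so that the Day 1 test counts, its window becomes that of footnote 3. The last row then meets both rules. The Screening/Baseline test remains, but that column opens at Day -30, and a test early in it is outside both 24-hour windows.

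**Dose, for context only.** "Patients will receive 10.5±1 mCi of radiotracer" (footnote 6), and the dosimetry table in section 1 gives 0.135 rem/mCi for the uterus: 0.135 × 10.5 = 1.42 rem, with 0.135 × 9.5 = 1.28 and 0.135 × 11.5 = 1.55 rem at the limits, excluding CT.

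**The case against.** The strongest reply is that a participant must satisfy section 3.2 as well as footnote 3. With Day 1 as the imaging day, which is the natural reading of an eligibility criterion, every qualifying test precedes Day 1 and so precedes the injection. The calendar also has a Screening/Baseline test in the same column as the eligibility check. Both rules and both calendar marks can be met with two tests, one on the day before and one on Day 1.

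This stands, and it rules out a stronger reading that a reader might infer: that a participant can meet the whole protocol with her only test done after exposure. The documents do not support that. It follows from footnote 3 taken alone, not from footnote 3 together with section 3.2 read literally.

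The reply has a cost, however. It relies on the reading under which the scheduled Day 1 test does not count towards eligibility, and it still leaves the order of that test and the dose unstated. A site that reads section 3.2 so that the Day 1 test counts gives up the protection.

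Three further points are fair. Taking the imaging day to be Day 2 or 3 is strained, though the missing definition does not exclude it. The SPECT/CT study in footnote 3 may be meant to include the injection, but no text says so and footnote 7 times the scan separately. The contrast with vital signs and ECG is only moderate evidence, because those are before-and-after measurements that need an anchor on each side.

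**Conclusion.** The point holds as a contradiction between stated rules on a participant-safety check. The rules use different reference points, neither of them the injection, and disagree on whether the Day 1 test counts. Footnote 3 by itself lets that test follow dosing by up to 2-4 h; section 3.2 read literally and the screening test mitigate this.

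Two figures should not be over-read. The 8.3% to 16.7% is a share of one footnote's window, not the chance of a late test; with section 3.2 read literally the corresponding share is zero. The 1.28 to 1.55 rem is a uterus estimate projected from animal biodistribution; it is not a fetal dose and does not depend on how the footnote is worded.

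The 8 to 14 h common window rests on the assumed 08:00 to 12:00 injection and on Day 1 being the imaging day. The contradiction itself needs only the latter. How many of the 10 participants the rule would apply to is not stated. The sample size and all analyses are unaffected.

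**What to change.** Reconcile section 3.2, the calendar row and footnote 3 into one rule used in all three places. The text should:

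- define the imaging day, or drop the term;
- name the reference event from which the interval is counted;
- state how the Day 1 test relates to radiotracer administration;
- state whether the Screening/Baseline test, the Day 1 test or both satisfy the eligibility criterion.

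The interval and the timing are for the sponsor to choose; none is proposed here. The cost is about one sentence in two places, section 3.2 and footnote 3. No test or visit is added, because both tests are already in the calendar, and nothing in section 7 has to change.

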¹¹¹In-XYIMSR-01. In 2015 Wichert and co-workers identified a promising dual-motif inhibitor of CAIX from a DNA-encoded chemical [25]. We subsequently improved upon this agent by replacing the IRDye750 portion of their molecule with the hydrophilic species 1,4,7,10-tetraazacyclododecane-1,4,7,10-tetraacetic acid (DOTA), which enables convenient radiolabeling with metal isotopes for positron emission tomography (PET), single photon emission computed tomography (SPECT), and radiopharmaceutical therapy [26, 27]. We have termed this agent XYIMSR-01 have previously reported our pre-clinical experience with an indium-111 labeled (¹¹¹In) version of the molecule [27]. SPECT imaging of immunocompromised mice bearing CAIX-expressing SK-RC-52 tumors revealed radiotracer uptake in tumor as early as 1 hour post-injection. Biodistribution studies demonstrated 26% injected dose per gram of radioactivity within tumor at 1 hour. At 24 hours post-injection, Tumor-to- blood, muscle, and kidney, ratios were 178.1 ± 145.4 , 68.4 ± 29.0 and 1.7 ± 1.2 , respectively. Retention of radioactivity was exclusively

observed in tumors by 48 hours, the latest time point evaluated. In total, imaging with ^{111}In -XYIMSR-01 enabled specific detection of ccRCC in this xenograft model, with pharmacokinetics surpassing those of previously described radionuclide-based probes against CAIX.

Dosimetry. Using the biodistribution data generated in the paper by Yang et al. we have estimated the human dosimetry for ^{111}In -XYIMSR-01 agent.

Target Organs	Organ Dose (rem/mCi)	Organ Dose (mSv/MBq)
Adrenals	1.60E-01	4.31E-02
Brain	3.82E-02	1.03E-02
Breasts	6.07E-02	1.64E-02
Gallbladder Wall	1.54E-01	4.15E-02
Lower Large Intestine	1.24E-01	3.36E-02
Small Intestine	1.38E-01	3.73E-02
Stomach Wall	1.47E-01	3.97E-02
Upper Large Intestine	1.21E-01	3.28E-02
Heart Wall	1.38E-01	3.74E-02
Kidneys	4.74E-01	1.28E-01
Liver	1.79E-01	4.84E-02
Lungs	3.43E-01	9.28E-02
Muscle	1.67E-01	4.51E-02
Ovaries	1.39E-01	3.74E-02
Pancreas	1.72E-01	4.65E-02
Red Marrow	1.00E-01	2.71E-02
Osteogenic Cells	1.47E-01	3.98E-02
Skin	6.19E-02	1.67E-02
Spleen	1.59E-01	4.30E-02
Testes	9.07E-02	2.45E-02
Thymus	1.23E-01	3.32E-02
Thyroid	1.14E-01	3.08E-02
Urinary Bladder Wall	1.29E-01	3.49E-02
Uterus	1.35E-01	3.66E-02
Total Body	1.34E-01	3.63E-02

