7.2 Secondary Objectives

Biodistribution and Radiation Dosimetry: A secondary objective of this study is to determine the biodistribution and radiation dosimetry of ^{111}In -XYIMSR-01. To allow for this, SPECT/CT images will be acquired at 2-4, 24 ± 1 hour, and 48 ± 1 hour post-injection. For the first three patients a total of three fields of view will be acquired and for the remaining 7 patients two fields of view will be acquired. Each SPECT acquisition will be acquired over a 20-30 minute period. The first time point acquisition for each field of view will include a high resolution CT. All other time points will be acquired with a low-dose CT.

The acquired PECT/CT images will be used to perform the biodistribution and radiation dosimetry calculations. Time-activity curves (TACs) demonstrating radiotracer activity as a function of time post injection (minutes) will be drawn for the whole body and the following organs: brain, breast, gallbladder, stomach, pancreas, heart wall, lung, liver, bladder, muscle, pancreas, red marrow, spleen, adrenals, upper large intestine, lower large intestine, small intestine, thymus, thyroid, testes and ovaries. Individual organ residence times will be calculated by fitting an exponential function to the TAC data and analytically integrating the fitted functions from zero to infinity. Organ specific mean radiation-absorbed dose estimates for ^{111}In -XYIMSR-01 will be calculated from the individual organ residence times. Reference organ mass values will be adjusted based on actual organ masses. The OLINDA software package will be used to determine the absorbed dose [28].

Characterization of Pharmacokinetics: The pharmacokinetic profile of ^{111}In -XYIMSR-01 will be determined as a secondary endpoint of the study. ~5 mL of blood will be collected in heparinized tubes at pre-dose, 5 ± 2 minutes, 10 ± 2 minutes, 20 ± 5 minutes, 30 ± 5 minutes, 1 ± 0.25 hour, 1.5 ± 0.25 hour, and 24 hours ± 1 hour, post-injection to estimate elimination half-life. The collected blood will be evaluated for total radioractivity, the ratio of free versus protein-bound radiotracer, and measurement of the relative percentage of radiotracer and its metabolites.

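### The elimination half-life rests on a single late blood sample at 24 h, so the plan cannot show whether a slower phase follows; the 48 h blood draw carries no PK tube

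*Combined protocol and SAP*

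**What the plan says.** Section 2.2 lists as a secondary objective "To characterize the pharmacokinetics of" the tracer, and section 7.2 says that the PK profile "will be determined as a secondary endpoint of the study". Footnote 4 of section 4 and the PK paragraph of section 7.2 give the same blood times: pre-dose, then 5, 10, 20 and 30 minutes, followed by "1±0.25 hour, 1.5±0.25 hour, and 24 hours ± 1 hour, post-injection to estimate elimination half-life". Each sample is to be measured for total activity and for "the ratio of free versus protein-bound radiotracer, and measurement of the relative percentage of radiotracer and its metabolites".

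The Pharmacokinetics & Imaging Timepoints table agrees that no PK blood is taken at the 2–4 h or 48 h scans. Footnote 10 has safety chemistry and a blood count that "will be collected at the end of 48 hour SPECT/CT imaging", with no PK tube mentioned.

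For the images, section 7.2 names a method: "Individual organ residence times will be calculated by fitting an exponential function to the TAC data". For blood it names none.

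**The concern.** Half-life is the stated reason for these samples. With one observation after the early cluster, the late phase of any fit is drawn through that observation. A sample at 24 h does show that clearance slows after the first two hours. It cannot separate one moderate late phase from a moderate phase followed by a slower one. The reported figure could then look precise, pass its own goodness-of-fit check and still not be the elimination half-life. A 48 h sample that was not taken cannot be recovered. Because no blood model is named, the choice of method can also move the answer.

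**Working it through.** **No figure to reproduce.** The plan gives no expected half-life, precision target or assay error. All curves and errors below are assumptions.

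**1. The gap.** From footnote 4 the cluster ends by 1.5 + 0.25 = 1.75 h, and the next sample may come at 24 − 1 = 23 h. That leaves at least 21.25 h with no PK sample. From the timepoints table the cluster ends by 90 + 25 = 115 min = 1.92 h, a gap of at least 21.08 h.

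**2. Can the planned times separate the two cases?** Take a curve with 70% at a 10-minute half-life and 30% at a single late half-life of 4, 5 or 6 h. Fit to it a three-phase curve whose slowest phase (12, 24 or 48 h) holds 90% of the 24 h level. The pairs agree within 0.9–1.6% at all seven planned times, yet differ 3.6- to 41-fold at 48 h.

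**3. Two-phase truth.** Single patient, two-phase log-scale fit, 10% lognormal error, 2,000 runs, half-life capped at 500 h. Assumed curves (fraction, half-life in h): (0.8, 0.25; 0.2, 6), (0.8, 0.3; 0.2, 8), (0.8, 0.5; 0.2, 12).

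| True late half-life | Planned, 5–95% | With 48 h sample |
|---|---|---|
| 6 h | 5.5–7.1 h | not needed |
| 8 h | 7.0–12.4 h | 7.5–8.8 h |
| 12 h | 8.5 h to no upper limit (21% of fits over 100 h) | 10.4–14.4 h |

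**4. Three-phase truth, slow fraction 3–5%.** Same method. Curves: (0.7, 0.2; 0.25, 1.5; 0.05, 15), (0.7, 0.2; 0.25, 2; 0.05, 20), (0.7, 0.3; 0.27, 3; 0.03, 30).

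| True | Planned median | Short by | Median with 48 h |
|---|---|---|---|
| 15 h | 6.8 h | 1 − 6.8/15 = 55% | 14.4 h |
| 20 h | 7.2 h | 1 − 7.2/20 = 64% | 19.0 h |
| 30 h | 6.4 h | 1 − 6.4/30 = 79% | 26.6 h |

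Misfit means a weighted residual sum of squares above the 95% chi-square point, with 7 − 4 = 3 df as planned and 8 − 4 = 4 df with 48 h. It is flagged in 4.5–5.7% of planned fits, which is the false-alarm rate. With a 48 h sample it is flagged in 60, 67 and 30%.

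**5. Three-phase truth, slow fraction 10–15%.** The fast phase is 0.7 at 0.2 h throughout. Medians are from two smaller sets of runs.

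| Intermediate; slow | Planned median | Short by |
|---|---|---|
| 15% at 1 h; 15% at 10 h | 8.2–8.4 h | 16–18% |
| 15% at 1 h; 15% at 12 h | 9.7–9.9 h | 18–19% |
| 15% at 1.5 h; 15% at 15 h | 10.7 h | 29% |
| 20% at 1 h; 10% at 15 h | 9.9–10.0 h | 33–34% |
| 15% at 1 h; 15% at 20 h | 14.6–14.9 h | 26–27% |

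Misfit is again flagged at about the chance rate. The size of the bias thus depends on the slow fraction, which is unknown.

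**6. What a 48 h sample gives directly.** Half-life = 24·ln 2 / ln(C24/C48), with the SE of the log ratio = √2 × error. For the 15 h curve in step 4, C24 = 1.650% and C48 = 0.544%. The log ratio is 1.109, so 16.636/1.109 = 15.0 h. At 10% error, 1.645 × √2 × 0.10 = 0.233, giving 16.636/(1.109 ± 0.233) = 12.4–19.0 h. Without noise, the 20 h and 30 h curves in step 4 give 19.9 and 27.1 h.

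**7. When that fails.** Call a patient not estimable if the observed log ratio is below 1.96 SE. The probability is Φ(1.96 − log ratio/SE). At an assumed 30% late error, SE = √2 × 0.30 = 0.424.

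| Curve | Log ratio | Not estimable |
|---|---|---|
| 12 h (step 3) | 1.386 | 10% |
| 15 h (step 4) | 1.109 | 26% |
| 20 h (step 4) | 0.835 | 50% |
| 30 h (step 4) | 0.614 | 70% |

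**8. The unnamed model.** For the 12 h two-phase curve, C1.5 = 0.2834 and C24 = 0.0500. A simple 1.5–24 h slope gives 22.5·ln 2 / ln(0.2834/0.0500) = 9.0 h, while the two-phase fit centres on about 12 h.

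**9. Windows.** Footnote 4 and section 7.2 give 20±5 min, 1±0.25 h and 1.5±0.25 h. The table gives 20±2, 60±25 and 90±25 min. The last two overlap by (60 + 25) − (90 − 25) = 20 min. This is a separate contradiction and does not cause the half-life problem.

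**The case against.** The strongest reply is that nothing in the documents shows a slow blood phase. If clearance has two phases and a late half-life near 6 h, the planned fit is adequate. The only kinetic evidence is in mice: section 1.1 reports a 24 h tumor-to-blood ratio of 178.1 and retention exclusively "observed in tumors by 48 hours, the latest time point evaluated". That suggests little late blood activity, so a 48 h tube may yield little. It would also be least informative where the possible bias is largest (50% and 70% not estimable at 20 and 30 h under 30% error). These points stand. They make every magnitude conditional and are the reason for a relabelling fallback.

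A second reply is that the images already reach 48 h, since section 7.2 plans curves of "radiotracer activity as a function of time post injection (minutes) will be drawn for the whole body and the following organs". Those curves may hint at a slow phase. They do not measure blood, and no blood-pool curve is named for the PK analysis. Nor do they separate tracer from metabolites, but a 48 h tube counted only for total radioactivity would not do so either.

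A third reply is that the stakes are low: this is one descriptive secondary endpoint in ten patients. That is correct, and it limits the weight of the point.

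What the replies leave standing is that the planned samples cannot test the two-phase assumption on which the half-life would depend, and the plan does not state that assumption.

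**Conclusion.** The point holds as a limit on what the schedule can show. With two phases, the planned half-life is adequate near 6 h and has no usable upper limit near 12 h. With a third phase it reads short by about 16–33% for slow fractions of 10–15% and by more than half for 3–5%, with no warning from the fit. These figures rest on the assumed curves and 10% error.

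Three stronger readings are not supported:

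- A reader might infer that the reported half-life will be wrong by half or more. That follows only from small assumed slow fractions, and whether a slow phase exists is unknown.
- A reader might infer that the 24 h sample is useless. If there are only two phases, it does identify the late half-life, precisely when that is short.
- A reader might infer harm to safety or dosimetry. No dose, stopping or dosimetry rule in the documents uses this half-life; dosimetry uses the image curves.

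The change is worth making because it is cheap and the sample cannot be recovered later. Confidence is moderate.

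**What to change.** 1. Add a heparinized PK tube of about 5 mL to the safety draw at the end of 48 h imaging. Report each patient's 24–48 h half-life with its interval, or 'not estimable' where there is no upper limit. The cost is 10 tubes and up to 10 × 3 = 30 measurements, with no new visit or draw. The downside is that 48 h blood may be near background. If only total radioactivity is measured at 48 h, the result is a total-activity half-life and should not be described as that of the parent tracer.
2. If no 48 h tube is taken, or its activity is not countable, label the result 'apparent half-life, 0–24 h'. This costs only wording.
3. In section 7.2, name the model for the blood data and state that actual collection times will be used. This also costs only wording.
4. Reconcile the sampling windows in footnote 4 and section 7.2 with the timepoints table, including the overlap between the 60- and 90-minute windows.
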